At the end of the surgery, the patients were referred to the PACU, where they were monitored again, and went through the pain assessment process using the visual analog scale (VAS) in relation to pain at rest and “movement” (the patient was asked to perform the forced cough movement), through a direct question with scale demonstration. Pain characterized as mild (0 - 2 VAS) received no medication, in addition to those already prescribed; pain characterized as moderate (3 - 7 EVA) received IV morphine at a dosage of 0.025 mg.kg⁻¹; and severe pain (8 - 10 VAS) received IV morphine at a dosage of 0.05 mg.kg⁻¹ every 01 h until analgesic control. To be considered able to be discharged from the PACU for clinical follow-up in wards, patients should reach a score ≥ 9 on the modified Aldrete Scale (Table 3) and have VAS pain scores ≤ 2 .

Upon arriving at the infirmary, patients were periodically evaluated at regular intervals in relation to the intensity of pain, with the help of a team of properly trained and qualified nurses. For patients who presented moderate-intensity pain (VAS $\geq 2 < 8$) or pain classified as severe (VAS ≥ 8), IV morphine was administered at a dose of 1 mg and 2 mg, respectively, according to a medical prescription. All analgesic medications used were recorded in the patient's medical record. 24 h after discharge from the PACU, in the ward, the patient was evaluated by the same examiner who performed the evaluation in the PACU, who again performed the stratification of pain by VAS and an evaluation with the McGill questionnaire.

During the entire hospitalization period of the study patients, the use of CNS depressant drugs (example: ketamine, droperidol, promethazine) and / or analgesic drugs that are not included in the study protocol was avoided. If any of the patients were medicated with such drugs, they would be excluded from the study to avoid bias in the statistical analysis. The data related to surgery (pre, trans and postoperative) were collected for statistical analysis, according to Annex II, in which, for example, the total duration of surgery in minutes was described; the total of intravenous fluids infused; the values of mean arterial pressure and heart rate in the pre, intra and postoperative period;

the presence or not, as well as the quantity, of PONV in the PACU and after 24h; presence or not of dizziness as a possible side effect, among others.

Outcomes

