The primary outcome was the assessment of postoperative pain using two different scales, the traditional visual analog scale (VAS) and the McGill Pain Questionnaire. The secondary outcome was the comparative analysis between the groups of opioid consumption in the postoperative period, evaluating both the total dosage of opioids used, as well as the time between the end of surgery and the request for the first analgesic rescue dose.

Other outcomes that were analyzed, apart from the variation in patients' hemodynamic data during the surgical times (pre, intra and immediate postoperative period), the degree of sedation was also evaluated using the Ramsay scale, and the presence of side effects such as nausea and vomiting, itching and dizziness. Other independent variables were analyzed, such as age, weight, body mass index, education level, profession, family income.

Ethical aspects and records

This study with the objective of preserving the patients' physical and psychological integrity followed the statements enunciated by the Declaration of Helsinki. All patients previously admitted to the study were clarified about the methodological process, the randomization and blinding process, the guarantee of confidentiality, about possible side effects of the interventions and also about the risks and benefits of participating in the study and the consent costs for participation in it. After clarifying any doubts and consenting to the patients' participation, the free and informed consent form (ICF) was signed, to which one of the copies was delivered to the patient and another copy was filed with the study researchers.

According to Resolution No. 466 of December 12, 2012, of the National Health Council, which addresses the guidelines and regulatory standards for research involving human beings, this study was approved by the Research Ethics Committee (CEP) of UNIFAL- MG under opinion number 3,334,050 on June 17, 2019 (ANNEX IV). This research was also recorded in the North American database for the registration of clinical trials, Clinical Trials (clinicaltrials.gov), under the protocol NCT04495374.

Statistical analysis

Descriptive analysis (median, mean and standard deviation) was performed for continuous variables that followed a standard distribution, and these were expressed in a table.

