When analyzing parametric variables, the t test was used, and in comparisons between groups, the t test was used for independent samples, and in the analysis of data at different points in time between patients in the same group, we chose to use the test. t paired.

When evaluating non-parametric variables, the Mann-Whitney test was chosen. To compare numerical measurements between the times in each group, the Wilcoxon test was used for the related samples. To assess qualitative variables, Pearson's chi-square test or Fisher's exact test was chosen.

All data obtained were digitized and analyzed using the Statistic® 7.0 software, with a significance level of 5% ($p < 0.05$). For the elaboration of statistical graphs, the program used was the GraphPad Prism version 5.00 (Trial) of 2007.

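### The plan describes no between-group test of haemodynamic change and no adjustment for the preoperative value; a baseline-adjusted comparison would be more precise, provided that reading precedes the tablet

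*Combined protocol and SAP*

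**What the plan says.** The Outcomes section lists, after the primary outcome (pain) and the secondary outcome (opioid use), a group of other outcomes that includes "the variation in patients' hemodynamic data during the surgical times (pre, intra and immediate postoperative period". The Evaluation procedures and measures section confirms that the data collected include "the values of mean arterial pressure and heart rate in the pre, intra and postoperative period".

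The Statistical analysis section gives two families of tests.

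- **Within a group, over time.** For parametric data, "in the analysis of data at different points in time between patients in the same group, we chose to use the test. t paired". For other data, "To compare numerical measurements between the times in each group, the Wilcoxon test was used for the related samples".
- **Between groups.** For parametric data, "in comparisons between groups, the t test was used for independent samples". For other data, "When evaluating non-parametric variables, the Mann-Whitney test was chosen".

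The section does not assign a test to any named variable or say at which times the groups are compared. It mentions no change-score comparison, group-by-time term, analysis of covariance, mixed model or baseline covariate.

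**The concern.** The outcome is worded as variation over time, and the trial's question is whether pregabalin alters that variation. The tests described for variation each look inside one arm. Both arms receive spinal anaesthesia, midazolam, intravenous fluid and, when needed, vasoactive drugs, so a within-arm change can reflect any of these and says nothing specific about pregabalin. A reader given one p-value per arm may be tempted to compare them, and a change that is significant in one arm only is not evidence that the arms differ.

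The between-group tests do answer a treatment question, but as described they do not use the patient's own preoperative value. With 55 patients analysed out of 102 planned, precision is scarce, and a covariate already collected is a cheap way to recover some of it.

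**Working it through.** **The plan's own figure.** The only sample size given, 51 per group, is for the primary pain outcomes. It comes with no effect size or standard deviation (SD), so it cannot be reproduced, and it does not bear on this outcome. The documents give no power or precision figure for haemodynamics.

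**Inputs.** Analysed numbers are 28 (placebo) and 27 (pregabalin), from the Experimental draw section. The 5% significance level is from the Statistical analysis section; two-sided testing is assumed. The correlation rho between the preoperative and a later value is not given; 0.3 to 0.7 is assumed.

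**Step 1: unadjusted comparison at one time.** The standard error of the difference, in SD units, is sqrt(1/28 + 1/27) = 0.27. This is also the standard error of a chance imbalance in the preoperative value. The difference detectable with 80% power is (1.96 + 0.84) × sqrt(1/28 + 1/27) = 0.756 SD. With no true difference, simulation of the unadjusted t test at 28 v 27 rejected in 5.0% of 20,000 runs, so its type I error is held.

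**Step 2: adjustment for the preoperative value.** Analysis of covariance multiplies the variance by 1 − rho², ignoring the small cost of estimating the slope. The equivalent unadjusted sample size is 55/(1 − rho²), and the detectable difference is 0.756 × sqrt(1 − rho²). A plain change score has variance factor 2 − 2rho. Power is for an illustrative difference of 0.5 SD.

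| Assumed rho | Adjusted variance factor | Equivalent N | Detectable difference, adjusted (SD) | Power, unadjusted | Power, adjusted | Power, change score |
|---|---|---|---|---|---|---|
| 0.3 | 0.91 | 60 | 0.721 | 45.8% | 49.3% | 34.7% |
| 0.5 | 0.75 | 73 | 0.654 | 45.8% | 57.2% | 45.8% |
| 0.7 | 0.51 | 108 | 0.540 | 45.8% | 73.8% | 66.8% |

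A change score gains nothing over the later value alone when rho is 0.5 or less, so the covariate form is preferable.

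**Step 3: what would happen if within-arm p-values were compared.** Suppose the true change is the same in both arms and each within-arm test has power p. The chance that exactly one is significant is 2p(1 − p): 0.50 at p = 0.5, 0.455 at p = 0.65 and 0.32 at p = 0.8. Simulation at 28 v 27 shows how this depends on the size of the common change, in SDs of the change:

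| Common change | Exactly one arm significant | Direct between-group test of change significant |
|---|---|---|
| 0 | 9.5% | 4.9% |
| 0.2 | 29% | 5.0% |
| 0.38 | 50% | 5.0% |
| 0.5 | 41% | 4.9% |
| 0.8 | 4% | 4.7% |

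These figures measure a misreading. They are not error rates of the plan as written.

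**Step 4: timing of the covariate.** The tablets were given on the ward during the two hours before surgery. The first blood pressure monitoring described is later, in the operating room. The documents do not time the preoperative reading against the tablet. If it followed the tablet it may already carry a drug effect, and adjusting for it could remove part of the effect being estimated.

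**The case against.** A reader might infer that the haemodynamic outcome is not compared between groups at all, or is compared incorrectly. The documents do not support that: between-group tests are named, and under random allocation an unadjusted comparison at one time is valid, only less precise. The Randomization section describes alternating allocation, so that validity is not assured here. That is a separate problem, and baseline adjustment does not cure it.

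A reader might also infer that the preoperative values go unused. Paired tests between times would naturally include them. Since no test is tied to a variable, an independent-samples test applied to changes is not excluded either. The point is that none is described.

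The most tempting inference is that the authors drew treatment conclusions from within-arm p-values. Nothing in the text says so, and the 32–50% discordance applies only to that hypothetical use, at a chosen range of power. With no change, or with a large one, discordance is far lower.

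Three further objections stand. The gain rests on an assumed correlation, and spinal block, fluids and vasoactive drugs may weaken it; at 0.3 the gain is slight. The outcome ranks below primary and secondary, and no section gives it a special safety role. Data collection stopped in September 2020 after analyses of the data, and the document is dated January 2021, so a model added now would be post hoc.

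**Conclusion.** The point holds as a modest gap in the analysis of a lower-ranked outcome. The plan describes tests of haemodynamic change only within groups, unadjusted tests between groups, and neither a between-group test of change nor use of the preoperative value as a covariate. The consequence is lost precision. The variance of the group difference could fall to between 0.91 and 0.51 of its unadjusted value for assumed correlations of 0.3 to 0.7, and by less if the true correlation is lower. The conclusion rests on that assumed range and on the preoperative reading preceding the tablet, which the documents do not establish. It does not show that the described tests are invalid or that any treatment claim was wrongly drawn.

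**What to change.** 1. Establish from the data collection form when the preoperative mean arterial pressure and heart rate were taken relative to the tablet, and state it.
2. If the reading came before the tablet, compare the groups at each intra- and postoperative time by analysis of covariance on group plus the patient's preoperative value. A mixed model with the same covariate is an alternative. Report the adjusted difference and its 95% interval.
3. If the reading came after the tablet, do not adjust for it. Report the unadjusted between-group difference with its 95% interval.
4. Present within-arm changes as description, without p-values.
5. Label the analysis post hoc if it is added after the data were analysed.

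The cost is a few sentences in the Statistical analysis section and a small re-analysis of data already collected. No new patients or measurements are needed, and the primary outcome, the secondary outcome and the sample size are unchanged.
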